## LIST OF ABBREVIATIONS

Commonly used abbreviations (such as units and abbreviations used for electrocardiogram assessments) are not included in this list.

Abbreviation	Definition
ADHD	attention deficit hyperactivity disorder
ADHD-RS-IV HV	ADHD Rating Scale Version IV Home Version based on DSM-IV criteria
AE(s)	adverse event(s)
ANCOVA	analysis of covariance
ATC	Anatomic Therapeutic Chemical
CSR	clinical study report
C-SSRS	Columbia Suicide Severity Rating Scale
DSM-IV	Diagnostic and Statistical Manual of Mental Disorders, Fourth Edition
DSM-5	Diagnostic and Statistical Manual of Mental Disorders, Fifth Edition
ECG	electrocardiogram
EOS	End of Study
ICH	International Conference on Harmonization
ITT	intent-to-treat
LS Mean	least-squares mean
MAPLV	Markedly abnormal post-baseline values
MedDRA	Medical Dictionary for Regulatory Activities
MI	multiple imputation
PCS	potentially clinically significant

Abbreviation	Definition
PERMP	Permanent Product Measure of Performance
PERMP-A	PERMP-number of PERMP problems attempted
PERMP-C	PERMP-number of PERMP problems correctly completed
PMM	pattern mixture model
PP	per protocol
PT	preferred term
RBC	red blood cell
ROC	Receiver Operating Characteristic
SAE(s)	serious adverse event(s)
SAP	statistical analysis plan
SKAMP	Swanson, Kotin, Agler, M-Flynn, and Pelham Rating Scale
SKAMP-CS	SKAMP-Combined Score
SOC	system organ class
TEAE	treatment-emergent adverse event
WBC	white blood cell
WHO	World Health Organization
WHO DRUG E	World Health Organization – Enhanced Drug Dictionary

## **1. PURPOSE OF THE STATISTICAL ANALYSIS PLAN**

The purpose of the analyses described in this document is to compare the safety and efficacy of dasotraline to placebo in pediatric patients with attention deficit hyperactivity disorder (ADHD).

The statistical analysis plan (SAP) is written with due consideration of the recommendations outlined in the most recent International Conference on Harmonization (ICH) E9 Guideline entitled Guidance for Industry: Statistical Principles for Clinical Trials [1] and the most recent ICH E3 Guideline, entitled Guidance for Industry: Structure and Content of Clinical Study Reports [2].

This SAP describes the populations that will be analyzed, the subject characteristics parameters, the efficacy parameters, and the safety parameters. The details of the specific statistical methods that will be used will be provided. If additional analyses are required to supplement the planned analyses described in this SAP, they may be completed and will be identified in the clinical study report (CSR). Table, figure, and listing specifications are provided in separate documents.

## **2. PROTOCOL SUMMARY**

### **2.1 Study Objectives**

The primary objective of this study is to evaluate the efficacy of dasotraline 2 mg/day compared to placebo on attention-deficit hyperactivity disorder (ADHD) symptoms in children (6 – 12 years of age), who weigh  $\leq 30$  kg, in a laboratory classroom setting as measured by the change from baseline at Day 15 in SKAMP Combined Score (SKAMP-CS).

The secondary objectives are to evaluate the efficacy of dasotraline 2 mg/day compared to placebo on ADHD symptoms throughout the day (12 to 24 hours post-dose) in children in a laboratory classroom setting and to evaluate the safety and tolerability of dasotraline 2 mg/day using physical examinations, 12-lead electrocardiograms (ECG), vital signs, adverse event (AE) reports, clinical laboratory results, and the Columbia – Suicide Severity Rating Scale (C-SSRS) Children's Assessment.

### **2.2 Overall Study Design and Plan**

This is a randomized, double-blind, placebo-controlled, parallel-group, efficacy and safety study in children with ADHD in a laboratory classroom setting. The study will target 100 subjects (50 per treatment group) in an attempt to have 88 subjects complete the study (assuming a 12% overall dropout rate). Completers will be defined as any subject who participates throughout the duration of the study, up to and including both visits 5 and 6.

The study will be comprised of 3 periods:

1. Period 1: Screening (up to 42 days) including a 3 - 5 day ADHD medication washout, if necessary, prior to Day -1;
2. Period 2: Double-blind randomized treatment with either dasotraline 2 mg/day or placebo for 14 days; and
3. Period 3: End of Study (EOS) visit (7 ( $\pm$  2) days after last dose)

Prior to the start of treatment (Day 1) and following the conclusion of the 14-day double-blind period (Day 15), subjects will undergo a full-day laboratory classroom evaluation in cohorts of up to 18 subjects. Each laboratory classroom day will include seven 30-minute simulated classroom sessions where trained observers will assess subjects using the Swanson, Kotin, Agler, M-Flynn, and Pelham (SKAMP) Rating Scale. In addition during each classroom session, a 10-minute

math test (Permanent Product Measure of Performance [PERMP]) will be administered to evaluate sustained attention and effort. The appropriate math level for each subject is determined based on results of the math pre-test administered during the laboratory classroom practice session at screening.

The primary efficacy endpoint will be the change from baseline to Day 15 in ADHD symptoms as measured by the mean SKAMP-Combined score, obtained from an average of the 7 SKAMP assessments collected across the 12-hour classroom day.

Safety and tolerability will be monitored throughout the study by physical and neurological examinations, 12-lead ECG, vital signs, AEs, clinical laboratory evaluations (hematology, chemistry, and urinalysis), and the C-SSRS.

**Screening:** The screening period will be completed within a maximum of 42 days prior to the first dose of study drug and will begin with acquisition of informed assent from the subject and informed consent from at least one of the subject's parents/legal guardians.

Subjects will be confirmed as meeting DSM-5 criteria for a diagnosis of ADHD. Subjects may be either currently untreated or receiving stimulant ADHD medication at Screening. On Day -7 the ADHD Rating Scale Version IV - Home Version (modified for investigator administration) (ADHD-RS-IV HV) will be completed and subjects will attend a half-day practice laboratory classroom session intended to familiarize them with classroom schedules and procedures related to SKAMP evaluations, PERMP tests, and other planned activities. Any subjects receiving stimulant medication for ADHD will discontinue that ADHD treatment for 3-5 days prior to Day -1 in order to ensure that there is at least a 72-hour washout before the assessment of ADHD symptoms on Day -1. The day before randomization, the subject's parent/legal guardian will be contacted by study site staff in order to confirm the presence of clinically significant ADHD symptoms since discontinuation of stimulant medication. Clinically significant is defined as an ADHD-RS-IV HV total score  $\geq 26$  following a minimum 72-hour washout from any prior ADHD treatment. Subjects who do not demonstrate clinically significant ADHD symptoms (i.e., ADHD-RS-IV  $\geq 26$ ) on Day -1 will be considered screen failures and will not be eligible for randomization.

**Double-blind Period:** On Day 1 subjects will return to the clinic in the morning and those meeting all inclusion and no exclusion criteria will be randomized (1:1) to receive 2 mg/day dasotraline, or placebo, and will attend classroom sessions in which they will be evaluated for ADHD symptoms using the SKAMP assessment. During this baseline classroom assessment (Day 1), subjects will be evaluated at regular intervals: approximately 8 AM, 10 AM, 12 PM, 2 PM, 4 PM, 6 PM, and 8

[figure not shown]
PM. Subjects will begin taking study drug on the evening of Day 1 (with or without food) after the final, 8:00 PM baseline classroom assessment. Subjects will take one dose each evening before bedtime for a total of 14 days. Study drug should be taken at approximately the same time each evening. The first dose of study drug may be administered in the clinic after all assessments are completed and before the subject leaves, or at home. On the night (Day 14) before the second classroom day, study drug must be taken at 8 PM plus or minus 30 minutes. During the double-blind period, the clinical site will attempt to contact the subject's parent/legal guardian daily with a reminder to administer study drug. A dosing diary will be provided to the parent/legal guardian to record the date and time of each administration of study drug. On Day 15 subjects will return to the clinic in the morning at 6:30 AM and classroom sessions will be started at approximately 8 AM, 10 AM, 12 PM, 2 PM, 4 PM, 6 PM and 8 PM to coincide with 12, 14, 16, 18, 20, 22, and 24 hours following the Day 14 dose.

**End of Study:** Seven ( $\pm 2$ ) days after the last dose of study drug, all subjects will return to the clinic and complete assessments. After the EOS visit, all subjects will be referred for continuation of their care as determined by the investigator. Additionally, for subjects who complete the study or discontinue for tolerability or lack of efficacy reasons, the sponsor will provide support for approved ADHD medication costs for up to 3 months after participation in the study, if deemed medically appropriate by the subject's healthcare provider.

A study schematic is presented in

Figure 1. Details of the study assessments and other procedures to be performed at each visit are presented in Appendix 14.1, Schedule of Events. If necessary, subjects may return to the clinic at any time for an unscheduled visit. The timing of events during a sample laboratory classroom day is provided in Appendix 14.2.

**Figure 1: Study Schematic**

### 2.3 Study Population

The subject population includes males and females ranging from 6 to 12 years of age, and in concert with standard practice guidelines, will be required to have a diagnosis of ADHD established by a comprehensive psychiatric evaluation that reviewed Diagnostic and Statistical Manual for Mental Disorders, Fifth Edition (DSM-5) criteria for ADHD (inattentive, hyperactive, or combined presentation). Subjects are required to weigh  $\leq$  30 kg since a 2 mg/day dose in such a group is expected to result in mg/kg levels similar to those demonstrated to be effective in children and adults. All specific inclusion and exclusion criteria can be found in the protocol, Sections 8.1 and 8.2.

### 2.4 Method of Assigning Subjects to Treatment Groups

After successfully meeting study entry criteria, subjects will be randomly assigned in a 1:1 ratio to 1 of the following treatments:

- 2 mg/day dasotraline (N = 50 subjects)
- Placebo (N = 50 subjects)

An Interactive Response System (IXRS) will be used to manage randomization on Day 1 and, if necessary, for emergency unblinding of treatment assignment during the study. The IXRS is an integrated web-based subject and drug management system.

Study medication will be assigned by an IXRS based on the randomization schedule. The IXRS will generate instructions on which medication number to assign to a subject.

## 2.5 Treatment Regimens

Under supervision from the subject's parent/legal guardian, subjects will self-administer the study drug on an outpatient basis for 14 days beginning the evening of Day 1. Study drug should be taken at approximately the same time each evening. The first dose of study drug may be administered in the clinic, after all assessments are completed, before the subject leaves, or at home. On Day 14, the night before the second classroom day, study drug must be taken at 8 PM plus or minus 30 minutes. All study medication doses will consist of 1 capsule per day taken by mouth.

## 2.6 Sample Size Determination

A post-hoc ANCOVA-LOCF analysis of data from the SEP360-305 laboratory classroom study was conducted to examine the effect of dasotraline 4 mg/day versus placebo in a subset of pediatric patients with ADHD aged 6-9 years old. This analysis showed an effect size in this subgroup of 0.95 (LS mean difference at Week 2 was 7.2 with a standard error of 2.2). Assuming a smaller effect size for dasotraline 2 mg/day vs. placebo than that of dasotraline 4 mg/day vs. placebo, an effect size of 0.7 was utilized for the sample size calculation.

The 0.7 effect size also derives from a data analysis showing that in a weight-adjusted dose range of 0.065 mg/kg to 0.115 mg/kg, the SKAMP effect size was observed to be 0.70. The weight adjusted dosing in the proposed study (SEP360-311) will likely range from 0.057 mg/kg to 0.125 mg/kg given that six year old females are expected to be the lightest subjects (CDC estimates 16 kg = 3rd percentile). Thus, the estimated effect size of .7 is a reasonable assumption and will be employed in the power and sample size calculation.

Therefore, assuming an effect size of 0.7 for dasotraline 2 mg/day compared to placebo on the primary efficacy endpoint of mean SKAMP-Combined score obtained from the average of 7 assessments collected across the 12 hour classroom day, 88 subjects (44 per treatment group) will provide 90% power to detect a treatment effect between dasotraline and placebo at the two-sided alpha level of 0.05, based on the two-sample t-test with equal variance procedure.

The study will target approximately 100 subjects (50 per treatment group) randomized to either placebo or dasotraline 2 mg/day in an attempt to have 88 subjects complete the trial (assuming a 12% overall dropout rate).

### 3. GENERAL ANALYSIS, REPORTING, AND PROGRAMMING CONVENTIONS

This section discusses general policies to be employed in the analysis and reporting of the data from the study. Departures from these general policies may be given in the specific detailed sections of this SAP. When this situation occurs, the rules set forth in the specific section take precedence over the general policies.

All continuous study assessments will be summarized by treatment group (2 mg/day dasotraline and placebo) and time point (as applicable) using descriptive statistics (n, mean, median, standard deviation, minimum, and maximum). All categorical study assessments will be summarized by treatment group and time point (as applicable) using frequency counts and percentages. All study data will be listed by subject, treatment group, and time point (as applicable).

Hypothesis testing, unless otherwise indicated, will be 2-sided and performed at the 5% significance level. When confidence intervals are presented, they will be 2-sided with a confidence coefficient of 95%. P-values will be reported to 3 decimal places if greater than 0.001. If less than 0.001, '<0.001' will be displayed. P-values and significance levels will be reported as 0.05 rather than .05.

No preliminary rounding will be performed; rounding will only occur after analysis. To round, the digit to right of last significant digit will be considered: if <5 then round down, if ≥5 then round up. Minimums and maximums will be presented with the same precision as the original data. Means and medians will be presented with one more decimal place than the precision of the data. Standard deviations will be presented with two more decimal places than the precision of the data. Percentages will be presented with one decimal place.

Medical history and AEs will be coded using the Medical Dictionary for Regulatory Activities (MedDRA) Version 19.0. Medications will be coded with the World Health Organization – Enhanced Drug Dictionary (WHO DRUG E, 2016 Q1 version).

All analyses will be performed using the SAS System® version 9.3 or higher.

The following general programming conventions will apply:

**Exposure days:** (Last dosing date – first dosing date + 1)

**Compliance:** [(Number of doses taken)/(number of doses planned)]\*100

**Duration days:** (End/resolution date – start/onset date +1)

**Study day:** (Date of interest – first dosing date + 1) if date of interest is on or after the first dosing date. (Date of interest – first dosing date) if date of interest is before the first dosing date.

## **4. ANALYSIS POPULATIONS**

The 3 analysis populations are defined below. Subjects will be analyzed based on the treatment to which they are randomly assigned. Identification of the subjects to be included in each analysis population will be determined prior to database unblinding. The database will be locked and unblinded after the SAP is signed and authorized, there are no outstanding data issues, and the final analysis populations are imported into the study database.

### **4.1 Intent-to-Treat Population**

The Intent-to-Treat (ITT) population is defined as all subjects who are randomized. The ITT population will be used for the efficacy analyses. Efficacy data will be analyzed according to the treatment the subject was randomized to receive.

### **4.2 Safety Population**

The safety population includes all subjects who are randomized and receive at least 1 dose of study medication. All safety analyses will be performed using the safety population.

Safety data will be analyzed according to the treatment the subject actually received, regardless of the treatment to which the subject was originally randomized. For subjects who inadvertently received treatment from more than one treatment arm due to site conduct error, the subject will be categorized by the treatment he/she received the most.

### **4.3 Per-Protocol Population**

The per-protocol (PP) population is defined as all subjects from the ITT population without any important protocol deviations (see Section 4.5). This supplemental efficacy population will be used to assess robustness of the primary analysis results.

### **4.4 Disposition of Patients**

Subject disposition will be summarized for all screened subjects, for each treatment group and overall. The following subject disposition information will be presented:

- The number and percentage of patients who were screened, who were screen failures, who were randomized, who completed the study, and who prematurely discontinued from the study
- The number and percentage of patients who discontinued prematurely, by reason for premature discontinuation

- The number and percentage of patients in the ITT, safety, and PP populations

In addition to these summaries, a listing by subject will be provided that shows treatment assignment, patient number, sex, age, race, reason for discontinuation, and any specific comments related to discontinuation.

#### 4.5 Protocol Deviations

Protocol deviations (PDs) will be collected during monitoring visits. Protocol deviations will be placed into, but not limited to, the following categories: prohibited concomitant medications, dosing, enrollment inclusion/exclusion criteria, laboratory, non-compliance, and others which are deemed to be study PDs. Each instance of a PD will be reviewed and determined to be important or minor before the study DBL.

A summary of important PDs will be provided as number (%) of subjects with at least 1 important PD and number (%) of subjects in each category in all randomized subjects. A listing by subject will also be provided that will include all PDs, deviation date, type, and any specific comments related to the deviation.

The following conditions, if met, would constitute an important PD. As such, any subject meeting one or more of these conditions would be omitted from the PP population. Important PDs are not limited to the list below. All protocol deviations within the monitoring report and the clinical database will be reconciled and adjudicated by the clinical team after the study is complete for the identification of all other important PDs.

	Category	Explanation
1	No proof of randomization or subjects mistakenly randomized	At Visit 4, there is no randomization number indicated on CRF field or subject mistakenly assigned randomization number.
2	Subject is non-compliant	Subject is not lost to follow-up and is <75% or >125% compliant with study drug.
3	Prohibited medications taken	Subject took any of the prohibited medications listed in Section 10.3.1 of the protocol during the study from screening through the EOS visit, unless the medication is clinically adjudicated as permissible.

4	Treated subject who did not meet inclusion/exclusion criteria	Subject failed one or more of the inclusion or exclusion criteria listed in Section 8 of the protocol, but continued in the double-blind period of the study.
5	Subject tests positive for substance abuse	Subject has one or more positive urine drug screen test at any visit during the course of the study.
6	Subject is unblinded during study	Subject is unblinded to treatment at any time during the course of the study.
7	Subject receives incorrect treatment	Subject's actual treatment received does not match randomized planned treatment.
8	Subject misses Day 15 visit	Subject is randomized and receives treatment, but is not present for the Day 15 classroom assessments

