## **7.4 Efficacy Outcomes**

### **7.4.1 Primary Efficacy Outcome**

The primary efficacy outcome is the change from baseline (Visit 4) at Day 15 (Visit 5) in ADHD symptoms as measured by mean SKAMP-CS obtained from an average of the 7 assessments collected across the 12 hour classroom day (12 to 24 hours post-dose).

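### Three per-protocol exclusion rules in SAP 4.5 stay open until the EOS visit, so an event after the Day 15 classroom can remove a completed primary-endpoint value from the supplemental PP analysis

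*SAP*

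**What the plan says.** The endpoint is fixed at Day 15. SAP 7.4.1 states: "The primary efficacy outcome is the change from baseline (Visit 4) at Day 15 (Visit 5) in ADHD symptoms", taken as the average of seven classroom assessments, the last at 8 PM. The last dose is on the evening of Day 14, and the EOS visit follows 7 ± 2 days after it.

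SAP 4.5 lists eight conditions that count as important deviations and remove a child from PP. Three of them are not tied to the endpoint:

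- Rule 3, use of any disallowed drug "listed in Section 10.3.1 of the protocol during the study from screening through the EOS visit, unless the medication is clinically adjudicated as permissible".
- Rule 5: "Subject has one or more positive urine drug screen test at any visit during the course of the study". The schedule includes a urine drug screen at Visit 6.
- Rule 6, unblinding at any point in the study.

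On the purpose of PP, SAP 4.3 says: "This supplemental efficacy population will be used to assess robustness of the primary analysis results". SAP 7.5.1 runs the primary analysis on ITT and repeats it on PP.

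**The concern.** A PP population for a Day 15 endpoint should leave out children whose Day 15 value may have been compromised by a deviation. An event on Day 17 or at the EOS visit cannot change SKAMP ratings already made, so excluding on it discards a valid observation without making the comparison cleaner.

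The loss may also not be random. Whether a family restarts ADHD treatment once dosing has ended plausibly depends on how the child was doing. If so, the rule selects on the outcome after it has been measured, possibly unequally by arm. At stake is the usefulness of PP as a robustness check: a gap between ITT and PP could be produced by the exclusion rule rather than by any weakness in the primary result.

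**Working it through.** **1. Timing.** Last dose Day 14; EOS at 14 + 7 ± 2, which is Day 19 to Day 23. Against the Day 15 classroom, the open window is 19 − 15 = 4 to 23 − 15 = 8 days.

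**2. What each rule catches in that window.**

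| Rule | Stated exception | Does it catch restarted ADHD treatment? |
|---|---|---|
| 3 | Clinical adjudication, no date criterion | Non-stimulants yes; stimulants unclear |
| 5 | None | Amphetamine products can; methylphenidate is not on the urine panel (Protocol Appendix III) |
| 6 | None | No; a separate route with no evident link to outcome |

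The uncertainty on rule 3 comes from the protocol. The rule points to Protocol 10.3.1, whose screening-to-EOS list refers to non-stimulant class agents. The corresponding list in the synopsis refers to stimulant class agents. Eligible children are untreated or on stimulant monotherapy (Protocol 8.1), so the conflict bears on the most likely restart.

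The general deviation review in SAP 4.5 does not rescue rules 5 and 6. The listed conditions are important deviations once met, and the closing adjudication step is there to find further important deviations beyond the list.

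**3. The plan's own figure.** SAP 2.6 states that "88 subjects (44 per treatment group) will provide 90% power". Its other inputs are the effect ("assuming an effect size of 0.7 for dasotraline 2 mg/day compared to placebo"), the test ("based on the two-sample t-test with equal variance procedure") and a two-sided alpha of 0.05. The noncentrality is 0.7 × √(44 × 44 / 88) = 0.7 × √22 = 3.28 on 86 degrees of freedom. Noncentral-t power is 0.901 at 44 per arm and 0.894 at 43, so 44 is the smallest sufficient number. 88 / 0.88 = 100 randomised. The figure reproduces and is not in dispute.

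**4. Precision lost.** The documents give no rate for these events. Assuming equal loss in both arms and an unchanged effect of 0.7:

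| Lost per arm | Children left per arm | PP power |
|---|---|---|
| 0% | 44 | 0.901 |
| 5% | 41.8 | 0.885 |
| 10% | 39.6 | 0.868 |
| 20% | 35.2 | 0.825 |

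**5. Shift of the placebo mean.** If m of 44 children average d points worse than the remaining 44 − m, the full mean exceeds the mean of the rest by d × m / 44. Dropping the m children moves the mean by that amount. With d = 5 (assumed):

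- m = 2: 5 × 2 / 44 = 0.23
- m = 5: 5 × 5 / 44 = 0.57
- m = 8: 5 × 8 / 44 = 0.91

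Lower SKAMP is better, so the placebo PP mean improves and the treatment difference shrinks. With losses in both arms and the same d, the net shrinkage is d × (m on placebo − m on dasotraline) / 44, which is zero if the losses are equal.

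For scale, SAP 2.6 reports a difference of 7.2 at effect size 0.95 in the earlier classroom study, implying an SD of 7.2 / 0.95 = 7.58. An effect of 0.7 is then 0.7 × 7.58 = 5.31 points. The shifts are 0.23 / 5.31 = 4%, 0.57 / 5.31 = 11% and 0.91 / 5.31 = 17% of the planned effect.

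**6. Selection acting in both arms.** Take normal outcomes with SD 1 and a true difference of 0.70, and let the chance of exclusion depend on the Day 15 outcome in the same way in each arm:

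| Placebo lost | Difference if the odds of loss double per SD worse | Difference if everyone above one cutoff is lost (extreme) |
|---|---|---|
| 5% | 0.69 | 0.62 |
| 10% | 0.68 | 0.56 |
| 20% | 0.66 | 0.48 |

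Differences are in units of the original SD. Under the milder model dasotraline loses 3.2%, 6.5% and 13.7%. Under the extreme model it loses 0.9%, 2.4% and 6.2%.

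**The case against.** The strongest reply is that little depends on this. ITT is primary and keeps every such value, PP is supplemental, no decision rule uses it, and missing-data sensitivity analyses are described separately. That stands, and it limits the severity. A reader might infer that a child loses the primary-endpoint value outright; the documents do not support that, since the value is lost only from PP.

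A reader might also infer that any child who resumes treatment after Day 15 is excluded. The text does not go that far. Rule 3 exclusions can be adjudicated away, its reach to stimulants is unclear, and a restarted methylphenidate product is not a listed urine analyte. The label of rule 5 speaks of substance abuse, which arguably leaves out a prescribed drug. Its operative text is broader, though, and lacks the allowance for prescribed medication that Protocol 8.2 gives to a positive screening test.

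A third inference would be that exclusions will be more frequent on placebo. That is plausible but unsupported: no restart rate is given for either arm. Rule 6 has no stated connection to symptom control, so the selection argument does not extend to it.

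Finally, adherence over the whole study is a coherent PP definition, since the protocol carries its medication restrictions through EOS. That justifies recording later events as deviations. It does not show that they bear on a Day 15 score.

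**Conclusion.** The wording gap is real and the consequence is minor. Rules 3, 5 and 6 each allow an event 4 to 8 days after the endpoint to remove a valid Day 15 value from PP. Rule 5 at Visit 6 is the clearest instance, rule 6 is equally unconditional but without an evident link to outcome, and rule 3 is conditional on adjudication.

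The ITT primary result is unaffected. If poorly controlled placebo children restart more often, the PP difference is biased toward zero: by 0.23 to 0.91 points for 2 to 8 of 44 children who are 5 points worse, with no such loss on dasotraline. In that scenario the rule makes a sound ITT result look less robust, so the inference that it would falsely favour dasotraline fails. The counts, the 5-point gap and the imbalance between arms are all assumptions. Only the timing and the rule wording come from the documents.

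**What to change.** In SAP 4.5, for PP exclusion only, count rules 3, 5 and 6 for events dated up to the end of the last Day 15 classroom session, with no exclusion on the Visit 6 urine screen. Keep later events in the deviation summary and listing. Because medication records carry dates, add a convention for medication first taken on Day 15 itself. Children who miss Day 15 need no cut-off, since rule 8 already removes them.

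Separately, the prohibited-medication lists in the protocol synopsis and in Protocol 10.3.1 must be reconciled so that rule 3 has a defined scope.

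The cost is a change of SAP wording and a date condition in the PP flag. Medication dates, deviation dates and visit-level urine results are already collected, and SAP 5.1 already separates post-treatment medications. The change should be made before PP membership is fixed ahead of unblinding.

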15.3.3. Important Protocol Deviations

Protocol deviations (PDs) will be collected during monitoring visits. Protocol deviations will be placed, but not limited to, into the following categories: concomitant medications, dosing, enrollment inclusion/exclusion criteria, laboratory, non-compliance, and other. Each instance of a protocol deviation will be reviewed and determined to be important or minor before the study DBL.

A summary of protocol deviations will be provided as number (%) of subjects with at least 1 protocol deviation and number (%) of subjects in each category in all randomized subjects.

The definition of important protocol deviations will be detailed in the study SAP and the subjects with important protocol deviations will be pre-identified (prior to unblinding of the study).

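### SAP important deviation 5 drops from the per-protocol set children whose screening-visit drug-screen positive the protocol accepts as due to prescribed medication

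*SAP*

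**What the plan says.** SAP 4.5 opens its table of important deviations with "The following conditions, if met, would constitute an important PD", and adds that "any subject meeting one or more of these conditions would be omitted from the PP population". Row 5 carries the category label "Subject tests positive for substance abuse". Its explanation column, which defines the condition, reads "Subject has one or more positive urine drug screen test at any visit during the course of the study".

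Two other statements in SAP 4.5 bear on how row 5 is used. First, "Each instance of a PD will be reviewed and determined to be important or minor before the study DBL"; Protocol 15.3.3 has the same sentence and leaves the definition of important deviations to the SAP. Second, the clinical team's adjudication after the study is there to find important deviations beyond those listed.

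Row 3 of the same table, on prohibited medication, has an escape clause: "unless the medication is clinically adjudicated as permissible". Row 5 has none.

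SAP 4.3 makes PP a supplemental efficacy population for judging the robustness of the primary result. The primary analysis is on ITT (SAP 7.5.1).

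**The concern.** The protocol foresees and permits the event that deviation 5 penalises. A child on a prescribed amphetamine product can enter the study, give a positive urine sample at Visit 1, have that result accepted, complete washout and be randomised without breaking any protocol rule. Deviation 5 as worded still removes that child from PP.

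Two things are at stake, both confined to PP. The set becomes smaller and less precise for a reason unrelated to adherence. It also loses children selectively by prior treatment, which SAP 7.5.3 lists as a subgroup factor to be tested for interaction with treatment. If the effect differs by prior treatment, PP and ITT would differ even with perfect adherence, and the difference could be misread as a sign about robustness.

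**Working it through.** **Can a permitted positive occur?**

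- Eligibility: Protocol 8.1, inclusion 5, admits untreated children and children on stimulant monotherapy. Of the four products it names, three are amphetamine-based (mixed amphetamine salts, lisdexamphetamine, dextroamphetamine); the fourth is methylphenidate.
- Sampling: a urine drug screen is scheduled at Visit 1 in Protocol Table 2, Protocol 11.5.1.1 and SAP 14.1.
- Panel: Protocol Appendix III includes amphetamines.
- Timing: Visit 1 runs from Day -35 to -8 in the protocol and from Day -42 to -8 in the SAP. It closes at Day -8 in both.
- Washout starts 3 to 5 days before Day -1: -1 - 3 = Day -4, and -1 - 5 = Day -6. In the usual sequence the Visit 1 sample precedes washout by at least 8 - 6 = 2 days.
- Acceptance: Protocol 8.2, exclusion 30, allows a child with a positive screen to continue if the investigator, after consulting the medical monitor, finds that prescribed medication explains it.

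**Does deviation 5 reach that sample?** SAP 2.2 makes screening a period of the study: "Period 1: Screening (up to 42 days) including a 3 - 5 day ADHD medication washout". Visit 1 is a scheduled study visit with a urine screen, and row 5 covers any visit. Row 4 (eligibility failure) does not apply, because the child satisfies exclusion 30. Row 5 alone removes the child.

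**The plan's own figure.** With an effect size of 0.7, two-sided alpha of 0.05 and a two-sample t-test, the noncentral t distribution gives 44 per group as the smallest size reaching 90% power (power 0.901). That is 88 completers, and 88 / (1 - 0.12) = 100 randomised. Both figures in SAP 2.6 reproduce, and this point does not challenge them.

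**What the loss could cost PP.** The documents give neither the share of children on amphetamine products nor the share testing positive, so the shares below are assumptions. With equal arms, in SD units:

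half-width of the 95% CI = t(0.975, N - 2) x sqrt(4 / N)

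| Removed (assumed) | N in PP | Half-width (SD) | Change | Power at 0.7 |
|---|---|---|---|---|
| none | 88 | 0.424 | n/a | 0.90 |
| 10% | 79.2 | 0.447 | +5.6% | 0.87 |
| 20% | 70.4 | 0.476 | +12.2% | 0.83 |
| 30% | 61.6 | 0.510 | +20.3% | 0.77 |

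In single counts, removing 1 child (N = 87) widens the interval by 0.6%, 5 children (N = 83) by 3.1%, and 10 children (N = 78) by 6.4%. All rows ignore other PP exclusions.

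**Case mix.** If a share s is removed and the effect in those children differs by d from that in the rest, the PP estimate moves from the ITT estimate by s x d. With assumed s of 0.10 to 0.30 and d of 0.2 to 0.4 SD, the shift runs from 0.10 x 0.2 = 0.02 SD to 0.30 x 0.4 = 0.12 SD, or 3% to 17% of the planned 0.7.

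**The case against.** The strongest reply is that nobody would apply the row this way. It sits under protocol deviations and its label speaks of substance abuse. A child with an accepted prescription has neither deviated nor abused anything. Every deviation is to be classed as important or minor before database lock, and populations are fixed before unblinding, so a sensible team would keep the child.

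This shows the likely intent, and a sensible outcome is possible. It does not change the operative text. The listed conditions are important by definition once met, and the later adjudication adds to the list; it is not described as releasing anyone from it. Row 3 shows that the authors wrote an exception where they wanted one. As it stands, either the literal rule is applied or unwritten discretion decides PP membership.

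A second reply is that the consequence is small. That stands. PP is supplemental and has no stated decision rule. Even the largest assumed shift, 0.12 SD, is about a quarter of the 0.51 SD half-width at 30% loss (0.12 / 0.51 = 0.24). At an estimate of 0.7 the interval would still exclude zero (0.7 - 0.51 = 0.19).

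A third reply is that the SAP describes 42-day screening and cites amendments up to protocol Version 4.00, while the supplied protocol has 35 days. The governing text of exclusion 30 could differ. This also stands as a caveat. The timing argument survives it, since Visit 1 closes at Day -8 in both documents.

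**Conclusion.** The point holds as an inconsistency between SAP 4.5 and the entry rules of the supplied protocol. Applied literally, deviation 5 removes correctly enrolled children from PP, selectively by prior treatment. The size is unknown; the ranges above rest on assumed shares and assumed differences in effect. The conclusion also assumes that exclusion 30 reads in the governing protocol as it does in the supplied one.

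A reader might infer more than the documents support:

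- That the treatment comparison is biased. The Visit 1 result precedes randomisation, so removal on that basis does not depend on arm. The ITT primary analysis and the sample size are untouched.
- That every Visit 1 sample precedes washout. Protocol 8 allows up to two rescreenings, including for insufficient washout, so a repeat Visit 1 could follow an earlier washout attempt. The sequence described is the usual one only.
- That row 3 needs a matching change, because Protocol 10.3.1 bans non-stimulant agents where the synopsis bans stimulants. That discrepancy is editorial. Section 10.3.1 itself bars any ADHD medication during washout, the synopsis bans stimulants through the end-of-study visit, and adjudication of other deviations remains open. Making stimulant use through that visit an automatic PP exclusion would also remove children for use after the Day 15 endpoint, a post-randomisation event that could relate to treatment response.

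**What to change.** Reword the explanation in row 5 of the SAP 4.5 table. A positive urine drug screen counts as an important deviation, except a positive at the screening visit that was accepted under exclusion 30 as the result of medication taken as prescribed. Positives at Day 1 or later continue to count. Check the cross-reference against the protocol version in force.

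The change must be made before PP membership is set and the data are unblinded. It costs one table row, with no new data collection and no protocol amendment. Row 3 can stay as it is.
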